2.2 RATIONALE

2.2.1 JUSTIFICATION OF BEHAVIORAL INTERVENTION METHODS

As Figure 1 shows, we have two facility-level interventions, one focusing on the HD provider care team, and one on patients. Both are posited to directly influence the cardiovascular stability of hemodialysis. See section 2.1.B for summaries of evidence regarding the effectiveness of checklists, team training, and peer mentoring in inpatient settings and chronic disease care.

With regard to specific behavioral intervention methods, Figure 1 illustrates how the interventions will address the cardiovascular stability of hemodialysis. Two theoretical approaches with strong empirical support in evidence-based interventions have guided development of the conceptual model.

Figure 1

I. Patient Activation Intervention

Socio-cognitive theory (SCT),⁹⁷⁻⁹⁹ is the key framework underlying the patient intervention. SCT emphasizes the predictive power of *self-efficacy*, or confidence in one's ability to perform an action, in the likelihood of performing that action. SCT has informed successful peer-based chronic disease interventions.^{100, 101} Further, peer mentors will use *motivational interviewing (MI)*¹⁰² principles that involve encouragement, exploration of feelings and personalized goal setting. MI is robust across clinical contexts,¹⁰³⁻¹⁰⁸ including peer mentoring focused on behavior change.^{19, 20} After influencing motivation and self-efficacy, we posit that the intervention will influence patient session instability prevention behavior, which will in turn influence fluid and HD adherence, both of which predict HD session stability. As Figure 1 shows, we posit a direct relationship between patients' behavioral involvement in session instability prevention activities and HD session stability. As Figure 1 shows, for patients, the behavioral outcomes (involvement in instability prevention activities) to be encouraged as part of the intervention (as well as post-intervention) include:

- i. *maintaining a diet that is low in sodium so as to reduce thirst and fluid retention;*
- ii. *maintaining a level of fluid intake that will lead to optimizing interdialytic weight gain, thereby resulting in a reduced need for excessive fluid removal during hemodialysis (fluid adherence);*
- iii. *attending regularly-prescribed hemodialysis sessions and remaining at the treatment for the full prescribed length (dialysis session adherence);*
- iv. *on an as-needed or continual basis, understand the importance of being agreeable to attending lengthened or supplemental hemodialysis sessions so as to ensure that treatments can be conducted at a lower ultrafiltration rate (<13 ml/kg/hour) (i.e., attention to session length/treatment time and ultrafiltration rate);*
- v. *actively participating in decision-making with their physicians and nurses regarding fluid removal targets (and achievement of appropriate post-hemodialysis target weight) and treatment times, with a goal of maximizing their cardiovascular stability; and*
- vi. *recognizing and reporting their symptoms of dialysis session instability / intradialytic hypotension (IDH) (e.g., dizziness, cramping, etc.) as soon as they begin to occur and promptly notifying facility staff so that appropriate interventions can be implemented (e.g., placing the patient in the Trendelenburg position) early.*

The intervention extends the peer mentoring program offered by the National Kidney Foundation (NKF), a patient-driven organization on our team. Peer Mentors are trained ESRD patients who volunteer to support other patients. Mentors can speak from experience about the challenges of life on hemodialysis; thus patients often view mentors as credible and accessible information sources.^{100, 109-111} Mentors can role model health behavior change as they share their experiences.¹¹⁰

II. Provider Education Intervention

The provider intervention is informed by the Theory of Planned Behavior (TPB), commonly used in practice change interventions for clinicians,^{112, 113} including patient safety checklist adoption.¹¹⁴ The TPB provides a model for predicting behavior based on behavioral intentions.^{115, 116} In the TPB, three belief-based constructs predict intention: (1) **attitude** toward the behavior; (2) **subjective norms**, i.e., the level of social pressure the person experiences to perform it; and (3) **perceived behavioral control (PBC)**, i.e., how easy the person thinks it would be to do. In a meta-analysis of healthcare providers behavior studies, there was a frequency-weighted mean correlation between TPB constructs and intention of $R^2 = 0.59$, and between intentions and behavior of $R^2 = 0.31$.¹¹³ The model posits that changes PBC and behavioral intentions will change providers' fluid management practice patterns, which will in turn reduce rates of dialysis session instability (Figure 1). The behavioral outcomes (fluid management practice patterns) to be encouraged among providers are also depicted on Figure 1. They include:

- vii. revisiting patients' fluid removal targets and treatment time;
- viii. involving patients in decisions regarding their fluid removal targets and treatment time;
- ix. focusing more on patients who are having difficulties with IDH so as to address these problems; and
- x. assessing patients' fluid volume status.

Various frontline staff members are engaged with the checklist intervention. While the checklist will be completed by the nurse, the checklist is designed as a tool to coordinate the involvement of multiple team members (please see attachment for full checklist content). For example, the checklist may involve obtaining information from the PCT for a data point which they typically gather (“Drop in SBP >=20 mmHg from sitting to standing?”) and will involve obtaining information from the patient (“Pt says he or she had symptoms of low BP?”) Furthermore, if implemented, the treatment considerations mentioned on the decision support component of the checklist also spark engagement with other staff members for their implementation. For example, the actions “place patient in modified Trendelenburg position,” and “more frequent BP measurement” will typically be implemented by PCTs. The dietitian (and often the nurse) is engaged with the following treatment consideration: “Reinforce dietary salt and fluid limits - seek dietitian input.” The social worker may also be engaged with the following action: “Stay on full prescribed time; do not miss treatments.” Physicians are also engaged with the following treatment consideration: “Review medications that affect blood pressure & consult MD as needed.”

2.2.2 SELECTION OF STUDY POPULATION

To accomplish rapid dissemination, and in keeping with the comparative effectiveness paradigm, this is a pragmatic trial; thus the effectiveness of the interventions will be assessed under the usual conditions in which they will be applied.¹¹⁷ The trial will take place as part of routine hemodialysis care, with low-intensity patient follow-up and use of outcome data already gathered routinely by facilities.¹¹⁸ Pragmatic intervention studies are most suited to support for healthcare-related decision making.¹¹⁷

Facility inclusion criteria include: (1) outpatient HD facilities, (2) at least 70 adult patients (≥ 21 years of age) who are permanent patients at the study facility (i.e., not from an outside clinic to receive isolation at the study facility or a visitor), (3) not involved in other Frenova research, (4) facilities with two to five stars in CMS’s Dialysis Facility Compare; (5) not in immediate jeopardy in previous two years; (6) not a facility in which the entire facility has been designated for isolation of patients with suspected or confirmed COVID-19; and (7) not a Kaiser Permanente facility. Dialysis facility staff will not be subjects in the research. These criteria were chosen to: protect the sample size (at least 70 adult patients), will not have its attention and resources devoted to other matters rather than the study (involvement in other research, one-star facilities, immediate jeopardy), and will not have a high proportion of patients suspected of having, or diagnosed with, COVID-19. Kaiser Permanente facilities are also excluded due to their additional administrative requirements. Randomization was stratified based on region (Midwest, Northeast, Southeast, Southwest), and the socio-economic status of the facility’s geographic area neighborhood (determined by the poverty rate in the county in which the facility is located; these were stratified into low/medium/high poverty levels) to account for potential differences in facilities.

We aim to include all non-vulnerable in-center patients at participating dialysis facilities. The trial is designed so as not to exclude anyone, including women and minorities to the extent they are represented at the dialysis facilities from the ages of 21 and older. We will only exclude vulnerable patients: those under 21 years of age; prisoners; those with a cognitive barrier (poor cognition or cognitive impairment); those deemed vulnerable by the Clinical Manager, Medical Director, and/or Social Worker (see Table 3: Screening for Patient Vulnerable Status), and those who are unable to comprehend the patient information sheet due to lack of facility in

English or Spanish. This will counter selection bias by ensuring that participants are representative of the full spectrum at a given facility. Selection bias is a risk in a peer mentoring intervention for a seriously ill population because patients who are comparatively less sick, and more motivated to manage their health actively, may be more likely to participate. The difficulty with such selection bias is that the study participants could be part of a subgroup of people who may have improved on their own, without the intervention. Therefore, improvements in outcomes may be erroneously attributed to the intervention. Our planned approach minimizes the likelihood of such mistaken conclusions. With regard to peer mentoring only, we will randomly select patients who are not vulnerable or have not opted out of the study in succession, until approximately a maximum of 30 patients in a facility finish peer mentoring (with partial data on at least 6 patients who start but do not finish). That is, every time a patient declines to participate, we will choose another patient randomly until the enrollment target is reached. Due to limited availability of peer mentors fluent in languages other than English, only English-speaking patients will be offered peer mentoring.

2.2.3 STUDY HYPOTHESIS

Our main study hypothesis is that hemodialysis session stability will significantly improve with either multimodal provider education or patient activation interventions, and that multimodal provider education will show a larger improvement. This hypothesis is based on our expectation that some hemodialysis patients might refuse or be unable to participate in peer mentoring, potentially leading to greater penetration of the provider intervention. We will test this main hypothesis and explore this potential explanation of any differential improvement as part of our planned sensitivity, mediation and moderation analyses.

2.3 RISKS AND BENEFITS

2.3.1 Potential Risks

This study has low risk to patients. The study uses current, accepted ways to prevent low blood pressure during dialysis. There is a very low risk that any patient's health data could be seen by people other than the research team. Sensitive patient information, such as medical information and medical history, will be collected as part of the study. Medical history includes conditions such as diabetes, high blood pressure, Hepatitis B or C, history of substance use, and mental health. The study is not collecting information about HIV or AIDS. However, there is a small risk that a diagnosis of HIV or AIDS will be included in the study data (see next paragraph). The study will collect information about COVID-19 diagnoses to examine the condition as a possible rival explanation for primary and secondary outcomes, and to account for patient absences from their home facility (e.g., in the context of dialysis adherence measures as a secondary outcome). All study data will be linked to a patient identifier and the researchers will make no attempt to link the information collected as part of the study to a patient's name or identity. Every effort will be made to keep patient information private. There are no known risks to the broader public or community.

As noted in the Data Elements List, FMCNA will provide medical diagnoses and the associated ICD codes extracted from the EHR. Information on co-morbidities will be extracted from the patient diagnosis section of the medical record. HIV/AIDS diagnoses will be excluded on the

basis of ICD9 and ICD10 codes provided by University of Michigan, with the list updated annually before October of each year. Although the risk of disclosure of HIV/AIDS diagnoses is minimal using this process, inadvertent disclosure may occur if this approach fails to identify all potential HIV/AIDS related diagnoses or if conditions associated with HIV/AIDS are included in the limited data set. In the event of inadvertent disclosure, such information will have been delivered to UM-KECC within a limited data set and will not be linked to any direct patient identifiers by the University of Michigan nor will it be included in any analyses. The patient information sheet will also include a statement regarding risk of disclosure of HIV/AIDS status. Additionally, sensitive diagnoses such as Hepatitis B, substance use, and mental health will be included in the limited data sets. The patient diagnoses will include additional diagnoses not included in the primary analysis, UM-KECC will restrict the diagnoses to medical co-morbidities of interest, including COVID-19.

2.3.2 Known Potential Benefits

If the research is beneficial, describe in detail any physical, psychological, social, legal, economic, or any other benefits to subjects that the PI foresees.

Note: Payment to subjects, whether as an inducement to participate or as compensation for pain and inconvenience, is not considered a “benefit.”

Study results will determine whether a provider education or a patient activation intervention can reduce the occurrence of a common complication of hemodialysis, intradialytic hypotension. This will inform hemodialysis care providers on whether to pursue these provider-focused or patient-focused interventions, both, or neither. People on hemodialysis will also have information to help them decide whether to become engaged in dialysis session stability, and the intervention will help them learn how to do so.

Peer-based healthcare approaches as trials have shown benefits in health outcomes^{23, 119-121} and behavior¹⁵⁻¹⁷—including complex health behaviors such as diet change.^{23, 24} Therefore, through an *innovative* application of peer mentoring, we aim to support the cardiovascular stability of hemodialysis by helping patients become more actively engaged in treatment and self-care decisions that affect their cardiovascular well-being. We will address patients' lack of information to help them meaningfully participate in cardiovascular stability-related decisions such as fluid removal targets, session length and frequency. Our preliminary studies showed that some patients already try to influence their treatment targets and speed so as to reduce distressing symptoms, and that ESRD patients share strategies for making hemodialysis more tolerable.¹²²

3 OBJECTIVES

3.1 STUDY OBJECTIVES

We will compare two interventions to improve the cardiovascular/hemodynamic stability of HD care by pursuing the following specific aims:

- **Aim 1** Conduct a cluster-randomized controlled trial (CRCT) to test and compare the effects of the above HD facility-level interventions on the primary outcome of dialysis session stability over an intervention period of 24 weeks and a post-intervention follow-up period of 12 weeks.
- **Aim 2** Test and compare the effects of the two HD facility-level interventions on secondary patient-centered clinical outcomes, including: patient symptoms, fluid adherence, dialysis adherence, quality of life, hospitalizations and mortality over the same timeframe.
- **Aim 3** Identify factors associated with successful implementation of the interventions, and ways in which implementation may influence intervention effectiveness.

3.2 STUDY OUTCOME MEASURES

3.2.1 Primary Outcome Measures

Dialysis session stability (primary outcome, Aim 1).

We define a dialysis session as unstable based on direct blood pressure measures that are routinely gathered during hemodialysis care. Secondary measures of the primary outcome include: (1) additional direct blood pressure measures; and (2) hospitalization or death on day in which dialysis was received.

Primary measure. The primary indicator of IDH based on direct blood measures after session start will be sitting Systolic blood pressure (SBP) falling below 100 mmHg (using lowest SBP during session) if starting SBP ≥ 100 .

Secondary measures of primary outcome. Secondary measures of IDH based on direct blood pressure measures will include: the lowest (minimum) valid SBP below 100 mmHg during the session if starting SBP is ≥ 100 , the number of SBP measurements < 100 mmHg (using raw blood pressure measures, time of blood pressure measure, and starting SBP) if starting SBP is ≥ 100 , and whether the sitting SBP falls below 90 mmHg (using lowest SBP during session) if starting SBP ≥ 100 .

Hospitalization or death on a day in which dialysis was received will be determined based on matching the date of cardiovascular or fluid-related hospitalization or death with the date/time of the administered dialysis session, and assessing the hospital discharge diagnosis or primary cause of death based on FMCNA records.

Justification of primary outcome. Our primary outcome is hemodialysis session stability, defined as intradialytic hypotension (IDH). The primary indicator of IDH based on direct blood measures after session start will be sitting Systolic blood pressure (SBP) falling below 100 mmHg (using lowest SBP during session) if starting SBP ≥ 100 . A fall of Systolic BP to less than 100mmHg signals a clinically important event during dialysis, with a higher probability of (patient-reported) symptoms¹²³ which equates to overtly suboptimal patient experience during dialysis. For example, in Meredith's 2015 study an SBP < 100 mmHg and/or reduction in SBP of 20% of baseline were the thresholds that maximized the probability that a session would result in an intervention (which typically occurs in response to symptoms).¹²³ Furthermore, the threshold of SBP < 100 mmHg was also shown to be detrimental both by Flythe et al.⁸² and Chou et al.⁸⁴ Furthermore, intervention at this threshold, even when asymptomatic, has the potential to prevent repetitive multi-organ tissue ischemia (e.g., a recent pilot study that studied cerebral

ischemia using noninvasive monitoring during hemodialysis).¹²⁴ Intervention at this SBP level is also likely prevent further decline to dangerously low levels of SBP<90mmHg.^{81, 82}

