2 INTRODUCTION: BACKGROUND INFORMATION AND SCIENTIFIC RATIONALE

2.1 BACKGROUND INFORMATION

2.1.1 NAME AND DESCRIPTION OF STUDY INTERVENTIONS:

I. Provider Education Intervention

Dialysafe IDH Checklist

Audience: Nurses, Patient Care Technicians (PCTs)

File Title: Provider Intervention (section 44 of IRB application)

A checklist application will be presented on provided tablet computers to nursing staff and PCTs at all clinics in the provider intervention arm. The checklist aims to identify patients at increased risk of intradialytic hypotension (IDH); it is to be completed by a nurse for each patient's dialysis treatment with verbal or documentation input from the PCT as indicated. The checklist has 4 items that may be associated with increased IDH risk: two pertaining to the past five treatments, and two regarding the date of the current session. The checklist is designed to focus nurse attention on clinical criteria related to IDH risk that change frequently. If any at-risk indication is selected in the checklist, a list of potential interventions to help prevent IDH will appear on the next screen of the checklist application.

See attached Checklist Application Overview.

Dialysafe Staff Training, part 1 of 4

Audience: Nurses, Patient Care Technicians, Dietitians, and Social Workers

File Title: Provider Intervention (section 44 of IRB application)

Staff training will begin by explaining the Dialysafe project goals and study design. Staff will refresh their knowledge on consequences of Intradialytic Hypotension (IDH) and the key role of fluid accumulation in the development of IDH. They will also identify their clinic's study group into which their clinic was randomized and training requirements related to their assigned study group. Finally, the role and responsibilities for each patient care staff member will be clearly defined.

Dialysafe Staff Training, part 2 of 4

Audience: Nurses, Patient Care Technicians, Dietitians, and Social Workers

File Title: Provider Intervention (section 44 of IRB application)

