During part 2, staff will consider the most vulnerable points in time for cardiovascular instability, which includes intradialytic hypotension (IDH). The training will review principles of weight and blood pressure measurement per existing FMCNA policy, including orthostatic blood pressure to evaluate fluid volume status and risk for IDH. The audience will be introduced to how the nurse will use the Dialysafe IDH prevention checklist to systematically evaluate every patient for IDH risk early in the session. If patients are found to be at risk for IDH, nurses are encouraged to choose from a list displayed on the checklist of possible actions to prevent IDH. If the patient's

fluid removal goal is decreased as a result, nurses are encouraged to contact the physician if indicated by the nurse's assessment to discuss the possibility of following FMCNA policy to add extra time to that session or add an extra session to achieve fluid balance per the physician's order.

Dialysafe Staff Training, part 3 or 4

Audience: Nurses, Patient Care Technicians, Dietitians, and Social Workers

File Title: Provider Intervention (section 44 of IRB application)

Part 3 begins with staff reflecting on their experience with the Dialysafe IDH prevention checklist. They will also review actions for increasing cardiovascular stability and assessing need for additional actions for patients at higher risk of intradialytic hypotension (IDH). Finally, staff will review their role in IDH prevention through important actions like regular review of estimated dry weight. They will consider times when they might discuss with the physician if it is appropriate to extend treatment time or add an additional day of treatment, and when they should consider steps such as additional medication review beyond the usual standard medication review or cool dialysate per physician order for higher risk patients to prevent IDH.

Dialysafe Staff Training, part 4 of 4

Audience: Nurses, Patient Care Technicians, Dietitians, and Social Workers

File Title: Provider Intervention (section 44 of IRB application)

Fifteen multiple-choice questions to measure learning of the material covered in parts 1-3.

See attached Staff training modules.

Dialysafe condensed Provider training for physicians, NPs and PAs

Audience: Physicians, nurse practitioners, and physician assistants

File Title: Provider Intervention (section 44 of IRB application)

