Checklist. A checklist application will be presented on provided tablet computers to nursing staff at all clinics in the provider intervention arm. The checklist aims to be completed by a nurse for each patient’s dialysis treatment. The checklist promotes: (1) systematic identification of patients who may be at increased risk of having IDH; and (2) considerations for preventive interventions to reduce IDH rates in hemodialysis clinics. To accomplish these aims, the checklist is designed to enhance: (1) critical thinking regarding factors which place patients at risk for IDH; and (2) increased focus on IDH prevention in routine hemodialysis care. The checklist has two main parts: (1) four questions to be answered with “yes,” “no,” or “data not available;” and (2) A list of potential treatment considerations for interventions, which are presented as reminders/prompts if any of the answers to the questions are “yes”. In line with the value of team training for patient safety,¹⁵² training will be provided to the care team, and to individuals through a self-study online curriculum. This holds promise for stimulating both collective ownership and for influencing providers’ subjective norms.

The checklist will be made available as an application on an Android tablet computer; the tablet computer, with the checklist application preloaded, will be provided to clinics as part of the

study. The tablet computer will be placed in a protective case that can withstand cleaning with bleach and facility staff will follow existing policies for disinfection. The checklist will not identify the patient or the staff member, but it will automatically log the facility, date, time, items displayed, and items clicked on a HIPAA-compliant server. The tablet will not need to be connected to the Internet to function; it will synchronize with the remote server when the Internet is available. If any screen other than the home screen is idle for more than 2 minutes, the system will revert to the home screen, which contains a blank checklist.

IX. Randomization and Stratification

To be in the study, facilities have been randomly selected. Randomization was stratified based on region, and the socio-economic status of the facility's geographic area neighborhood (determined by the poverty rate in the county in which the facility is located; these were stratified into low/medium/high poverty levels) to account for potential differences in facilities.

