Session-level variables to be assessed for potential mediation effects include: (1) treatment time delivered; (2) average session UFR; (3) cooled dialysate used; (4) sodium modeling used; (5) ultrafiltration modeling used; (6) ultrafiltration variability for whole session, or up until incident of IDH (if IDH occurs) (difference between the highest and lowest UFR, standard deviation of the UFR measures, the square root of the mean squared differences of successive UFR measures); (7) sitting-to-standing difference in SBP (orthostasis at beginning of session); (8) starting SBP; (9) slope of changes in SBP over 30 minute intervals for whole session, or up until incident of IDH (if IDH occurs); (10) values and times of lowest and highest SBP readings as a measure of range of SBP during the dialysis session; (11) patient request re: fluid removal at this session; (12) fluid adherence (inter-dialytic weight gain) at this session; (13) previous achievement of post-dialysis target weight; and (14) previous session instability.

Sensitivity Analyses. In addition to the sensitivity analyses described above, we will examine the effect that patient compliance/non-compliance rates, i.e., percent of patients who accept peer mentoring and checklist adherence for provider intervention, have on the results. The sensitivity analyses aim to assess the robustness of the conclusions based on the analyses of the primary outcome – specifically to determine whether the findings hold under different methods of defining the primary outcome. Thus we will conduct sensitivity analyses for the secondary measures of session instability described above. As part of this, because we will know the dates and causes of hospitalization and death by cardiovascular- or fluid-related causes, we will identify those events that took place on days in which dialysis was administered. Accordingly, we will conduct a sensitivity analysis of the primary outcome of dialysis session stability both with, and without, those events on dialysis days included. For the primary outcome analyses, we will also conduct a sensitivity analysis without the sessions of patients who begin that session with a sitting pre-dialysis SBP of 100-110 MmHg and whether the sitting SBP falls below 90 mmHg (using lowest SBP during session) if starting SBP ≥ 100 .

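### The provider checklist can prompt extra blood pressure readings in one arm while the primary outcome is the lowest reading, and no planned analysis equalises or reports reading frequency

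*Combined protocol and SAP*

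**What the plan says.** **Outcome.** Section 3.2.1 calls a session unstable on the basis of "sitting Systolic blood pressure (SBP) falling below 100 mmHg (using lowest SBP during session") when the starting SBP is at least 100. The readings come from routine care, and no fixed reading schedule is stated. One secondary measure is "the number of SBP measurements < 100 mmHg (using raw blood pressure measures, time of blood pressure measure, and starting SBP"); no denominator is given.

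**Checklist.** Section 2.2.1 (Provider Education Intervention) names "more frequent BP measurement" among the treatment considerations on the checklist and says technicians will typically carry it out. The list is conditional: "If any at-risk indication is selected in the checklist, a list of potential interventions to help prevent IDH will appear on the next screen" (section 2.1.1). It is also optional: "nurses are encouraged to choose from a list displayed on the checklist of possible actions to prevent IDH" (section 2.1.1, staff training part 2), and section 4.1 VIII describes it as "A list of potential treatment considerations for interventions, which are presented as reminders/prompts". Only provider facilities (cells A and B) have the checklist. Section 6.2.1 plans its use for the 24-week intervention period.

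**Analysis.** The session-level covariates in section 11.4 are weekday, shift, blood flow, dialysate flow and dialysate composition. The blood-pressure sensitivity analyses are an SBP <90 definition and a run "without the sessions of patients who begin that session with a sitting pre-dialysis SBP of 100-110 MmHg". A mediator list includes "slope of changes in SBP over 30 minute intervals for whole session". The third secondary analysis compares percent IDH between phases. The fidelity metrics in sections 6.5 and 11.4 do not include readings per session.

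**The concern.** One intervention can change how intensively its own primary outcome is measured. If flagged patients in cells A and B are read more often, more of their dips below 100 mmHg will be recorded even if their pressures match those of control patients. The planned effect is only 3.4 to 4.3 percentage points (section 11.2), so a small measurement difference could matter.

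The main hypothesis expects the larger improvement from provider education (section 2.2.3), and this artefact would work against it. A null provider result could then mean either no benefit or closer monitoring, and nothing in the planned analyses would show which. Comparisons between phases are exposed too, because checklist use is planned for one phase only.

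**Working it through.** **1. Does any planned analysis deal with reading frequency?**

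| Planned item | Effect on reading frequency |
|---|---|
| Session-level covariates (11.4) | Number of readings not included |
| SBP <90 definition (11.4) | Still uses the minimum of all readings |
| Excluding starts of 100-110 (11.4) | Still uses the minimum of all readings |
| Count of readings <100 (3.2.1) | Can rise as readings are added; no denominator |
| 30-minute SBP slope (11.4) | Candidate mediator; does not redefine the outcome |
| Phase comparison (11.4) | Same percent IDH |
| Fidelity metrics (6.5, 11.4) | Flagged share by checklist session, but not readings taken |

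The checklist log carries no patient identifier (section 4.1 VIII), so it cannot be linked to an individual patient's readings.

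**2. Direction.** Take one pressure course and a set R of readings, and let R' contain R plus extra readings. Then min(R') ≤ min(R), so the indicator of a minimum below 100 stays the same or changes from no to yes. With pressure unchanged, the artefact can only raise detected IDH in the provider group.

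**3. Reproducing Table 5.** Inputs from section 11.2: 60 patients per facility, 10 facilities per group, ICC 0.10, alpha 0.05 (taken as two-sided).

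- Design effect = 1 + 59 × 0.10 = 6.9
- SE = sqrt(2 × SD² × 6.9 / 600) = 0.01213 for SD 0.08, and 0.01517 for SD 0.10
- Power = Φ(D/SE − 1.96)

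| D | SD | Computed | Table 5 |
|---|---|---|---|
| 0.034 | 0.08 | 80.0% | 80% |
| 0.034 | 0.10 | 61.1% | 61% |
| 0.040 | 0.08 | 90.9% | 91% |
| 0.043 | 0.10 | 80.9% | 81% |

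**4. Illustrative attenuation.** Replace D by D − b, where b is over-detection in the provider group. This assumes that D describes the effect at equal reading frequency and that extra readings prompt no clinical response.

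| b (points) | D=0.034, SD 0.08 | D=0.043, SD 0.10 |
|---|---|---|
| 0 | 80% | 81% |
| 0.1 | 78% | 79% |
| 0.5 | 67% | 71% |
| 1.0 | 51% | 59% |

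Example: (0.034 − 0.010)/0.01213 − 1.96 = 0.02, and Φ(0.02) = 0.51.

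**5. What b might be.** The documents do not give it. A simulation of 240-minute sessions, with every input assumed, was calibrated to 20% IDH at 30-minute readings.

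- No clinical response, 20-50% of sessions flagged, 25-50% uptake, re-reading every 15-20 minutes: b = 0.1 to 1.6 points.
- Central case (30% flagged, 50% uptake, 15 minutes): 0.6 to 1.1 points.
- Uptake of 10% with 20-30% flagged: 0.1 to 0.2 points.
- Central case with a response in re-read sessions that raises later readings: net change of −0.3 to +0.5 points at 3 mmHg, and −0.9 to +0.1 at 5 mmHg.

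The last line spans zero, so the net sign is open.

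**6. Would a 30-minute grid be enough?** Only if usual care reads at least that often. With 60-minute usual readings assumed, a grid taking the reading nearest each 30-minute mark still left 0.6 to 0.9 points of over-detection. The interval has to come from the trial's own data.

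**The case against.** **The differential is inferred.** It rests on one phrase in a list illustrating staff roles, and the action is one optional choice for flagged patients. Staff training reviews blood pressure measurement under existing company policy (section 2.1.1). If that policy already asks for closer readings in at-risk patients, control facilities would do the same and the gap would shrink. The policy, the full checklist and the Data Elements List are attachments or outside documents not available here. This stands, and it is why no size can be claimed.

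**Responding to a reading is the point of the intervention.** Sections 2.1.4 and 3.2.1 present early action as the way to prevent worsening, so assuming no response is the less natural choice. This also stands. The power figures in step 4 are illustrations and should be read alongside the response scenarios in step 5.

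**The error is conservative and other outcomes are available.** Symptoms, recovery time, hospitalization and mortality do not depend on reading counts, and checklist adherence will be examined. These help interpret a null result, but they do not show whether the primary result was attenuated.

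**A grid discards genuine readings below 100**, which section 3.2.1 regards as important even without symptoms. That is a reason to keep the grid analysis supportive; it does not argue against having one.

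**Conclusion.** The point holds as a gap in the planned analyses. One arm's intervention may raise the number of readings that feed a lowest-reading outcome, and the plan neither equalises nor reports that number. A provider benefit in (A+B) vs (C+D) may be attenuated. The size and net direction cannot be derived from the documents. The illustrative losses (80% to 78%, 67% or 51%; 81% to 79%, 71% or 59%) rest on assumed over-detection of 0.1, 0.5 or 1.0 points and no clinical response.

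A reader might infer three stronger conclusions, none of which the documents support:

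- *The provider comparison is biased and underpowered.* Uptake, flagged share, usual interval and existing policy are unknown, and a modest clinical response brings the net change to zero or below.
- *Extra readings could produce a spurious provider benefit.* With pressure unchanged, added readings cannot reduce detected IDH, so they cannot do this in (A+B) vs (C+D). For B vs C the direction is uncertain, because mentored patients are encouraged to alert staff promptly, which may also trigger readings.
- *The primary endpoint should be replaced.* The lowest recorded SBP is a reasonable pragmatic outcome, and a supportive analysis is enough.

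This is a cheap improvement of minor to moderate priority.

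**What to change.** Keep the lowest of all readings as the primary outcome and add three items to the analysis plan before unblinding:

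1. Report blood pressure readings per session by arm and by period (baseline, intervention, follow-up).
2. Prespecify one sensitivity analysis that builds IDH (<100 and <90) from a common time grid of the time-stamped readings, applied in all arms and periods. Set the grid interval no finer than the usual interval seen in the pooled baseline data. Allow at most one reading per mark within a fixed tolerance window, use no reading twice, and state the rule for empty marks.
3. Express the secondary count of readings <100 as a proportion of readings taken or of grid readings.

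Interpret a null or adverse provider result alongside these and the outcomes that do not depend on reading counts.

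**Cost:** plan wording and some programming, using raw readings and times already planned for a secondary measure. The grid misses brief true dips in every arm, and prompted readings near a mark may still be picked up, so the analysis is supportive only. Care and the primary endpoint do not change.
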